UNIVERSIDADE DA CORUÑA

Grupo de Investigación en Gerontología y Geriatría

Study Protocol and Statistical Analysis Plan

Protocol Official Title: **Low-volume Cycling Training Improves Body Composition and Functionality in Older People With Multimorbidity: a randomized controlled trial**

ClinicalTrials.gov ID: [Not yet assigned]

Date: 6th April 2021

Grupo de Investigación en Gerontología y Geriatría ©
Universidad de A Coruña

INTRODUCTION

Aging is a risk factor for most chronic diseases, and the presence of more than two diseases (i.e., multimorbidity), which is frequent in almost two out of three older adults, has been related to an increased risk of disability and frailty, a decrease in quality of life, and mortality (Pedersen, 2019). Physical activity (PA) acts as a nonpharmacological intervention and regular physical activity (rPA) reduces rates of all-cause mortality, compresses morbidity, decreases healthcare costs, and has relatively minimal adverse effects compared to drugs (Fiuza-Luces et al., 2013).

It has been estimated that 27.5% of the world's population in 2016 did not meet the recommendations established for the member states of the World Health Organization (WHO) for health-enhancing physical activity. Furthermore, recent studies showed that moderate-intensity physical activity may be sufficient for reducing the risk of all-cause dementia and that some of the protective benefits of physical activity for older adults (Cunningham et al., 2020). It seems indispensable to study adequate doses of exercise for older people who often have low levels of physical activity and fitness, who spend a large amount of time sitting down, and whose multimorbidity keeps them away from exercising.

OBJECTIVES

To study the effects of perception-regulated low-volume and low-to moderate intensity training on body composition, hemodynamic parameters, and functional performance in older adults with multimorbidity.

MATERIAL AND METHODS

Study design

This longitudinal and prospective study conducted between September and December 2019, is a 2 x 2 randomized controlled trial using a two-group design (exercise vs. control) and two repeated measures (pre- vs. postintervention). This study is performed following the CONSORT (CONsolidated Standards of Reporting Trials) 2010 guideline.

Study setting and participants

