Participants are recruited between September and October 2019 at the Gerontological Complex La Milagrosa (A Coruña, Spain), consisting of a daycare center and a nursing home.

Inclusion criteria: (a) men and women aged 65 and older, (b) users of a care setting—daycare patients or nursing home residents, and (c) a score < 5 in the Global Deterioration Scale (GDS; Reisberg et al., 1982), from no cognitive decline to moderate cognitive decline.

Exclusion criteria: (a) physical limitations or musculoskeletal injuries that could affect cycling training performance; physical exercise contraindicated by the physiotherapist and verified by the medical doctor according to the medical register of each participant; (b) heart failure with a functional class according to the New York Heart Association (NYHA) Classification of NYHA III and IV; (c) the presence of acute pain that does not allow exercise training; (d) recent acute

myocardial infarction (in last 6 months) or unstable angina; (e) uncontrolled hypotension; (f) uncontrolled arterial hypertension ($>180/100$ mmHg); (g) active cancer treatment with chemotherapy; (h) patients with an active pacemaker and/or uncontrolled block; (i) diabetes mellitus with acute decompensation or uncontrolled hypoglycemia; or (j) any other circumstance that precludes individuals from completing the training intervention.

24 participants will be recruited and randomly placed into two groups: the exercise group (EG, n=12) and the control group (CG, n=12). A stratified permuted block randomization is employed that accounted for the GDS score, sex, and type of institutionalization. A nurse and a medical doctor enrolled and assigned participants to intervention.

Intervention

Cycloergometers

The Gerontological Complex La Milagrosa features a kinesiotherapy room equipped with three MOTOMed®muvi cycle ergometers (Fig. 1) adapted for older people. These cycle ergometers have the ability, through electric motors, to provide resistance to oppose cycling and, on the other hand, to passively move the limbs of the trainees. This movement system allows even subjects with loss of functional ability to mobilize (bipedestation or walking) to perform the activity from their wheelchair or geriatric chair.

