Therefore, a cycling cadence is fixed between 25 and 30 rpm for all sessions since that cadence is comfortable for every participant. Researchers adjust the resistance on the motorized cycle to increase the external load until it reached the level required to reach the intensity of effort programmed by the OMNI-RPE (Guidetti et al., 2011). The six weeks are programmed in the form of two intensity- differentiated training phases of three weeks. In the first training phase (i.e., the first three weeks), participants are requested to cycle simultaneously with the upper and

lower limbs at an intensity equivalent to a perception of 3 (i.e., easy to somewhat moderate) on the OMNI-RPE (0-10).

Control of adverse events was measured through the assessment and monitoring of vital signs before, during (within the first 10 minutes), and after the intervention sessions. Vital signs [heart rate (per minute), systolic and diastolic blood pressure (in millimeters of mercury, mm Hg), and oxygen saturation (in percentage)] were monitored by a nurse and a medical doctor using mobile finger pulse oximeters.

Throughout the training, evaluators are responsible for postural control and patient symmetry parameters controlled through the cycle ergometer screen.

The body posture of the participants in the chair in front of the machine is controlled considering the measurements of the appropriate joint angles in the knee, through a rule of ergometry. Two types of chairs are used for the performance of the activity, one conventional chair, and a geriatric chair in case the patient needs it to move.

For sitting, conventional geriatric chairs are used, seeking to respect the angles of the knee joint corresponding to a 152° extension, a 110° flexion, and a Range of Movement (ROM) of 42°. For the geriatric armchair, the values are extension 144°, flexion 105°, and ROM 39°.

Finally, it is established as a final criterion to consider the participant to complete at least 80% of the scheduled sessions (14 out of 18 sessions).

Participants (experimental and control group) are evaluated to examine the changes in body composition, functional performance, and resting cardiovascular state. Furthermore, participants are monitored physiologically during each session (heart rate and blood pressure) to control any possible adverse effects.

Measures

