Pre- and post-intervention assessments are made on all subjects of the sample (control and experimental group). Pre-intervention data were collected one week before the start of training, while post-intervention data were recorded at the end, after six weeks of intervention.

Socio-demographic variables

Age (years) and gender.

Body composition evaluation

Bioimpedance analysis (Inbody 270): body weight (kg), height (cm), muscle mass (MM), fat mass (FM), and FM percentage. Waist circumference (WC, cm) is taken at end-tidal using a measuring tape to the nearest 0.1 cm, midway between the lowest rib and the iliac crest, which corresponded with the level of the umbilicus. Body mass index (BMI) is established by the Quetelet index: $BMI \text{ (kg/m}^2\text{)} = \text{mass (kg)} / \text{height (m)}^2$.

Figure 3. InBody 270

Hemodynamic parameter evaluation

The baseline hemodynamic state is characterized by storing the mean of the three lowest values for thirty seconds of heart rate (HRrest, mm Hg) and oxygen saturation with a finger pulse oximeter; blood pressure by the auscultator method using a properly calibrated mercury column sphygmomanometer flexible cuff of the appropriate size and a stethoscope; three systolic (SBPrest) and diastolic blood pressure (DBPrest) measurements are recorded at 1-minute intervals. Mean blood pressure (MBPrest) is calculated as follows:

$$\text{MBP} = \text{DBP} + 1/3 (\text{SBP} - \text{DBP}).$$

Functional evaluation

- a) Frailty. Assessed by Fried et al. (2001), based on the presence or absence of 5 specific and phenotypic components (1) unintentional weight loss: at least 4.5 kg in the past year; (2) self-reported exhaustion, identified by 2 questions from the modified 10-item Center for Epidemiological Studies-Depression scale; (3) weakness: grip strength in the lowest 20% at baseline, adjusted for sex and body mass index; (4) slow walking speed: the slowest 20% at baseline, based on time to walk 4.6 m, adjusting for sex and standing height; and (5) low physical activity: the lowest 20% at baseline, based on a weighted score of kilocalories expended per week.
- b) The Performance-Oriented Mobility Assessment (i.e., POMA; Tinetti, 1986), which measures balance (i.e., POMA-B) and gait performance (i.e., POMA-G) and the total score (i.e., POMA-T).

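### On its natural reading, the SAP summarises oxygen saturation by the three lowest oximeter readings in 30 seconds, a lower-tail value that tends to read low and is sensitive to artefact

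*SAP*

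**What the plan says.** The Objectives section names the effect of training "on body composition, hemodynamic parameters, and functional performance in older adults with multimorbidity", so hemodynamic measures are study outcomes. The Intervention section says that participants in both groups are "evaluated to examine the changes in body composition, functional performance, and resting cardiovascular state"; the quantity wanted is therefore a resting level. Under Measures, "Pre- and post-intervention assessments are made on all subjects of the sample (control and experimental group").

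The definition itself is under Hemodynamic parameter evaluation, where the baseline state is represented as follows: "storing the mean of the three lowest values for thirty seconds of heart rate (HRrest, mm Hg) and oxygen saturation with a finger pulse oximeter". The same sentence then treats blood pressure differently: "three systolic (SBPrest) and diastolic blood pressure (DBPrest) measurements are recorded at 1-minute intervals", with no selection of the lowest.

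No other section gives saturation its own summary rule, a sampling rate, a signal-quality check or a way to reject artefact. The Intervention section mentions saturation again, but only as safety monitoring around the training sessions. The section Data management and statistical analysis plans to analyse changes both within and between groups.

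**The concern.** Keeping the lowest few values is a reasonable way to find resting heart rate, because the slowest beats in a short window are plausibly the most rested ones. That argument does not carry over to saturation. Readings disturbed by finger movement, poor contact or a weak pulse tend to fall in the lower tail, and the rule keeps only that tail.

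Two things are at stake. The reported level would sit below the resting level by an amount that depends on how noisy the trace is. A change in signal quality between visits could also look like a change in saturation. The exposure is greatest for the within-group changes that the SAP plans to analyse. With 12 participants per group, avoidable measurement noise is also unwelcome.

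**Working it through.** **Inputs from the SAP.** Three lowest values, a 30-second window, the same rule in both arms and at both visits, 12 per group. The SAP states no figure for saturation, so there is none to reproduce.

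**Assumptions (none given in the SAP).** True saturation 97%; independent normal readings rounded to whole points and capped at 100; 3 to 30 readings per window; within-window SD 0.5 or 1.0 point; 0, 1 or 3 artefactual readings, each 5 points low; 40,000 simulated windows per case.

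**Quantity.** With ordered readings x(1) ≤ x(2) ≤ … ≤ x(n), the stored value is L = [x(1) + x(2) + x(3)] / 3, and its bias is E(L) minus the true value.

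**Step 1: bias of L in points** (SD 0.5 / SD 1.0)

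| Readings | No artefact | One artefact | Three artefacts | Median, three artefacts |
|---|---|---|---|---|
| 3 | 0.00 / 0.00 | -1.67 / -1.66 | -5.00 / -5.00 | -5.00 / -5.00 |
| 6 | -0.31 / -0.70 | -1.92 / -2.22 | -5.00 / -5.00 | -2.50 / -2.50 |
| 10 | -0.51 / -1.07 | -2.08 / -2.48 | -5.00 / -5.00 | -0.20 / -0.55 |
| 30 | -0.96 / -1.66 | -2.33 / -2.88 | -5.00 / -5.00 | 0.00 / -0.07 |

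Without artefact, the mean and the median of all readings have bias of about 0 throughout. With three readings L is simply their mean, so nothing is lost. With 30 readings, three artefacts fill L completely (-5.00), while the mean of all readings moves by 3 × 5 / 30 = 0.50.

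**Step 2: correlated readings.** With 30 readings around 95% and a lag-1 correlation of 0.5, the bias is -0.89 at SD 0.5 and -1.60 at SD 1.0. Varying the correlation from 0 to 0.8 at SD 1.0 gives -1.66 to -1.40. On a very quiet trace (SD 0.2, correlation 0.8) the bias is under 0.1.

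**Step 3: between-group contrast.** Let D = (exercise post - exercise pre) - (control post - control pre). A bias that is equal in both arms at each visit cancels in D, even if it differs between visits. Within one arm it does not cancel. With 30 correlated readings as in Step 2, a fall in noise SD from 1.5 to 1.0 moves the bias from -2.40 to -1.60, an apparent gain of 2.40 - 1.60 = 0.80 points with true saturation unchanged.

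Simulated with 30 independent readings at SD 0.5 and artefacts of 5 points:

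- With artefact equally frequent everywhere, the bias in D is -0.01. The SD of an individual's measured change, with true saturation held fixed, rises from 0.25 (no artefact) to 1.48 at 2% of readings and 2.01 at 5%.
- With artefact absent only in the exercise arm after training, D is spuriously 0.84 (2%) or 1.91 (5%).
- With the median, D is 0.00 in every case.

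**Step 4: precision under ordinary noise.** With 30 readings, SD 1.0 and correlation 0.5, the measurement SD is 0.49 for L and 0.31 for the plain mean, a ratio of about 1.6. That ratio covers measurement error alone. If the true SD of change between people is s (assumed), the SD of observed change is √(s² + 2 × measurement SD²):

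- s = 1: 1.22 against 1.09, about 11% more
- s = 1.5: 1.65 against 1.56, about 6% more
- s = 2: 2.12 against 2.05, about 3% more

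**The case against.** The sentence can be parsed so that the three-lowest rule governs heart rate only, with saturation as a second stored item. In support, the heart rate and blood pressure variables carry a rest label and saturation does not. This reading is possible but less natural, and it leaves saturation with no summary rule at all. Either way the sentence needs clarifying.

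A reader might infer that the variable records artefact instead of resting saturation, or that every stored value is too low. The SAP does not support either. It gives no reading count and no noise level. With three readings, or a flat trace, the rule does no harm, and the larger biases need many readings or assumed artefact.

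A reader might also infer that the trial's saturation comparison is biased. It is a randomised comparison with one rule for both arms and both visits, so a common shift cancels. Nothing in the SAP suggests that signal quality would change differently by arm. The loss of precision under ordinary noise is also modest, as Step 4 shows. All of this stands, and it limits the size of the point. It does not make the rule suitable for saturation, and it does not protect the within-group changes.

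Finally, the study ran from September to December 2019 and the SAP is dated 6 April 2021, so a new definition cannot alter what was stored. That also stands and limits the fix.

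**Conclusion.** The point holds as a minor one. On the natural reading, the SAP fixes resting saturation by a rule suited to heart rate, and with more than three varying readings that rule estimates a lower-tail value. Under the assumptions above and without artefact, the average bias is 0 with three readings, under 0.1 point on a very quiet trace, about 0.3 to 1.1 points with 6 to 10 readings, and about 0.9 to 1.7 points with 30 readings at SD 0.5 to 1.0. The direction follows from the definition; the size cannot be fixed from the SAP.

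The between-group difference in change is biased only if signal quality changes differently by arm. Otherwise the rule shifts the level and adds some noise. Within-group change is open to any shift in signal quality between visits. Saturation is one hemodynamic outcome among many and does not appear in the trial's title.

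**What to change.** State whether the three-lowest rule applies to saturation. Restrict it to heart rate, and define resting saturation as the median (or mean) of all readings in the 30 seconds. The median is the more robust to isolated artefact, provided there are enough readings: with six readings of which three are bad, it too is 2.5 points low. If the full readings were kept, recompute saturation from them at both visits in both arms.

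If only the three-lowest mean was stored in 2019, label the variable 'lowest saturation over 30 s' and draw no conclusion about resting saturation from it.

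The cost is a sentence in the measurement definition and, where the data allow, a recalculation. The downside is that the full readings may not be recoverable, in which case only the relabelling applies.

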Data will be presented as the median and interquartile range for ordinal variables and the estimated marginal mean \pm standard deviation (SD) for continuous variables. The effect of the intervention will be analyzed employing nparLD (robust rank-based analysis of longitudinal data in factorial experiments) from the RStudio software package for nonparametric variables. Changes within and between groups will be analyzed by employing mixed models for repeated measures designs with the module GAMLj, which uses the R formulation of random effects as implemented by the lme4 R package in Jamovi software. The mixed models are a modern class of statistical models that extend regular regression models by including random effects parameters to account for dependencies among related data. We have chosen mixed models analysis as we expect a within-subject dependency in the variables measured before and after the intervention. Compared to traditional analyses that ignore these dependencies, mixed models provide more accurate (and generalizable) estimates of the effects, improved statistical power, and non-inflated Type I errors.

Duration of the project

	2019					2020	2021
	Jan-Aug	Sept	Oct	Nov	Dec	Jan-Dec	Jan-Dec
1. Project preparation and methodology							
2. Recruitment							
3. Baseline assessment							
4. Intervention (6 weeks per user)							
5. Post-intervention assessment							
6. Data analysis							
7. Dissemination							

References

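### Does showing continuous outcomes as estimated marginal mean ± SD, with no interval named for the group-by-time contrast, call for a change to the SAP?

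*SAP*

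**What the plan says.** The rule for showing results is one sentence in the SAP section on data management and statistical analysis. It opens "Data will be presented as the median and interquartile range for ordinal variables and the estimated marginal mean" and attaches to that mean a "standard deviation (SD) for continuous variables". It does not say whether the SD is the raw one or one derived from the model.

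Inference has its own sentence: "Changes within and between groups will be analyzed by employing mixed models for repeated measures designs with the module GAMLj". The reason given for the model is that "we expect a within-subject dependency in the variables measured before and after the intervention", and the section adds that "mixed models provide more accurate (and generalizable) estimates of the effects, improved statistical power, and non-inflated Type I errors".

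The design, described under Study design, is a trial "using a two-group design (exercise vs. control) and two repeated measures (pre- vs. postintervention"). The arms are "the exercise group (EG, n=12) and the control group (CG, n=12"). The Measures section plans assessments before and after the intervention for everyone in both groups. The SAP names no model covariates, and no standard error, confidence interval or confidence level for any effect.

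**The concern.** Two things look wrong.

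1. **The pairing.** The uncertainty of an estimated marginal mean is a standard error or a confidence interval. An SD measures how much people differ from one another and belongs beside an observed mean. Putting the two together mixes a model result with a description of the sample, and the kind of SD is left open.
2. **The missing interval.** The result that answers the trial's question is the difference between arms in pre-post change. Its precision depends on the correlation between the two visits, and neither cell SDs nor cell standard errors carry that information. The SAP chooses a mixed model because of this dependency, yet its sentence on presentation gives no place to the quantity in which the dependency shows.

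If only the table of cell means and SDs were published, a reader could compute the difference in change but could not tell how precisely it was estimated. In a trial of 24 people that would be a real loss.

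**Working it through.** The SAP gives no SD, correlation, effect size or confidence level, so there is no figure of its own to reproduce. Everything below is in units of a common SD.

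**Inputs.** n = 12 per arm (Study setting and participants); two groups and two visits (Study design); equal SD in every cell and complete data (assumed); pre-post correlation ρ of 0.3 to 0.9 (assumed, since the SAP gives none).

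**Step 1: is the marginal mean different from the observed mean?** A model with group, time and their interaction has four fixed effects for four cells. With complete data and no covariates, each marginal mean is the observed cell mean. Random-intercept fits to simulated complete data confirmed this for the two cells compared, with a largest gap below 1e-14. On the plan as written, the display is therefore observed mean ± SD.

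**Step 2: how far is the SD from the standard error?** SE of a cell mean = SD/√12 = 0.289 SD, so SD/SE = √12 = 3.46. The 95% half-width for a cell mean is 2.074 × 0.289 = 0.60 SD (t, 22 df). The factor 3.46 is the ordinary relation between an SD and a standard error at n = 12. It is not an error in any reported number.

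**Step 3: what would a missed visit do?** Suppose one person in an arm lacks the post visit and had a baseline d SD below the mean of the other 11. The mixed model then moves that arm's post mean from the observed mean by ρ·d/12. With d = 1 (assumed), the shift is 0.3/12 = 0.025 SD at ρ = 0.3 and 0.9/12 = 0.075 SD at ρ = 0.9. The marginal mean and the observed mean part company, but only slightly for a single missed visit.

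**Step 4: the difference in change.** SE = SD·√(2(1−ρ)·2/12) = SD·√((1−ρ)/3); half-width = 2.074 × SE.

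| ρ (assumed) | SE (SD units) | 95% half-width (SD units) |
|---|---|---|
| 0.3 | 0.483 | 1.00 |
| 0.5 | 0.408 | 0.85 |
| 0.7 | 0.316 | 0.66 |
| 0.9 | 0.183 | 0.38 |

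Simulated mixed-model fits gave mean standard errors of 0.47, 0.40, 0.31 and 0.18 SD, in line with the formula. One table of cell means and SDs is compatible with every row, so the interval cannot be read from that table.

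**Step 5: is the interval lost?** The group-by-time term of the planned model comes with its own standard error. If its t statistic or an exact p-value is reported, SE = |difference in change| / |t|, with the difference taken from the displayed means (this works poorly only when the difference is close to zero). The width at ρ = 0 is 2.074 × √(1/3) = 2.074 × 0.577 = 1.20 SD. That describes an analysis ignoring the correlation, which the SAP explicitly sets aside.

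**The case for a change.** The strongest case for a change has three parts.

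- **Complete data may not hold.** The Intervention section sets a criterion of at least 80% of sessions completed, so some non-completion is foreseen, and there is no rule for missed visits. Randomization is stratified by GDS score, sex and type of institutionalization. If those factors enter the model, marginal means can depart from observed means and the SD no longer matches its mean.
- **Effect intervals belong in an SAP.** How the main contrast will be reported is not something normally left to a protocol.
- **The remedy is cheap.** It needs one sentence and one table column, from models already planned.

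All three are fair as comments on drafting. The first is conditional: the SAP names no covariates and plans both assessments for everyone, and Step 3 puts the effect of one missed visit at less than a tenth of an SD under its assumptions. Even then the SD remains correctly labelled. The second is an omission rather than a misstatement. The presentation sentence reads most naturally as the rule for descriptive summaries by type of variable, and the analysis of change is planned in a separate sentence. The third shows that clearer wording would cost little, but not that following the present wording would produce a wrong result. The spread of half-widths from 0.38 to 1.00 SD comes wholly from the assumed correlations. The SAP gives no target effect or SD by which to call either end informative or uninformative.

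**Conclusion.** The observation is accurate: the SAP pairs a marginal mean with an SD without saying which SD, and it does not promise a confidence interval for the difference in change. No change to the plan follows. With both visits observed for all 24 participants and no covariates, the display is the observed mean ± SD and the issue is one of labelling. The contrast and its standard error are standard output of the planned mixed model, and an analyst reporting "Changes within and between groups will be analyzed by employing mixed models for repeated measures designs" would ordinarily give them. The model, its estimate, its test and its Type I error are the same whichever way the table is labelled.

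This rests on two conditions: complete or nearly complete post-intervention data, and publication of the mixed-model result itself alongside the cell summaries. With substantial missing visits or added covariates, the report should make clear that the SD is the raw one. That is a matter for the table's footnote and does not alter the analysis.

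### For outcomes sent to nparLD, the intervention test is a group-by-time rank contrast with no baseline adjustment: valid, but less efficient than rank ANCOVA unless the pre-post correlation is high

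*SAP*

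**What the plan says.** Under Study design, the SAP describes a randomised trial "using a two-group design (exercise vs. control) and two repeated measures (pre- vs. postintervention". Study setting and participants gives the size: "24 participants will be recruited and randomly placed into two groups: the exercise group (EG, n=12) and the control group (CG, n=12". Under Measures, "Pre- and post-intervention assessments are made on all subjects of the sample (control and experimental group", so a baseline value is planned for everyone.

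Data management and statistical analysis says that the intervention effect will be analysed "employing nparLD (robust rank-based analysis of longitudinal data in factorial experiments) from the RStudio software package for nonparametric variables". The same paragraph opens: "Data will be presented as the median and interquartile range for ordinal variables". It does not list which outcomes count as ordinal or nonparametric. Functional evaluation, item b, describes the POMA, "which measures balance (i.e., POMA-B) and gait performance (i.e., POMA-G) and the total score (i.e., POMA-T"; these scores are natural candidates.

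Mixed models are named for changes within and between groups, on the ground that "we expect a within-subject dependency in the variables measured before and after the intervention". No baseline covariate, ANCOVA or other baseline adjustment is named anywhere. The SAP states no alpha, effect size, target power or pre-post correlation.

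**The concern.** With two groups and two visits, a factorial rank analysis treats the baseline score as one level of the time factor. The intervention effect is then the group-by-time interaction, in effect the difference between arms in mean change of pooled ranks. Baseline is subtracted with a fixed weight of one, whatever the correlation between visits. When that correlation is moderate, the subtraction adds more noise than it removes. A baseline-adjusted test lets the data set the weight.

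Functional performance is a named objective, functionality is in the trial title, and 24 participants leave little precision to spare. The SAP defends the mixed models partly by their power under within-subject dependency; the rank route does not make the best use of that same dependency.

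**Working it through.** **Inputs.** From the SAP: 12 per arm, two arms, two visits. Assumed because the SAP gives no value: two-sided alpha 0.05; pre-post correlation ρ of 0.5, varied from 0.3 to 0.9; effect d of 0.5 to 1.2 SD of the score; no dropout. The SAP has no power figure to reproduce.

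**Step 1: variances (score SD = 1).**

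- Change contrast: 2(1 − ρ). At ρ = 0.5 this is 1.00, the same as ignoring baseline.
- ANCOVA: 1 − ρ². At ρ = 0.5 this is 0.75.
- Ratio: 2(1 − ρ)/(1 − ρ²) = 2/(1 + ρ). This is 1.33 at ρ = 0.5, 1.18 at 0.7, 1.11 at 0.8 and 1.05 at 0.9. The penalty fades as ρ rises.

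**Step 2: normal approximation at ρ = 0.5.** Power ≈ Φ(d / (s√(2/12)) − 1.96), with s the square root of the variance above. For d = 1.0:

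- Change: 1/0.408 − 1.96 = 0.49, so 68.8%.
- ANCOVA: 1/(0.866 × 0.408) − 1.96 = 0.87, so 80.7%.

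The gap is about 12 points. It is 6.2 points at d = 0.5 (23.1% against 29.3%), 11.9 at d = 0.8 (50.0% against 61.9%) and 8.8 at d = 1.2 (83.6% against 92.4%).

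**Step 3: simulation on ranks.** There were 20,000 trials per cell, with bivariate normal latent scores cut to 13 or 5 ordered levels. The interaction was coded as the between-arm contrast of changes in pooled ranks with unequal variances, referred either to chi-square (1 df) or to a Welch t. The comparator was ANCOVA on ranks. Power (%) at ρ = 0.5:

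| Levels | d | Contrast, chi-square | Contrast, Welch t | Rank ANCOVA |
|---|---|---|---|---|
| 13 | 0 (type I) | 6.5 | 4.9 | 5.1 |
| 13 | 0.5 | 23.3 | 19.8 | 25.0 |
| 13 | 0.8 | 46.4 | 41.9 | 52.2 |
| 13 | 1.0 | 63.3 | 59.0 | 71.6 |
| 13 | 1.2 | 77.8 | 74.0 | 85.3 |
| 5 | 0 (type I) | 6.5 | 5.1 | 5.2 |
| 5 | 0.5 | 19.9 | 16.8 | 21.7 |
| 5 | 0.8 | 39.9 | 35.6 | 46.0 |
| 5 | 1.0 | 55.4 | 50.6 | 64.3 |
| 5 | 1.2 | 69.9 | 65.6 | 79.5 |

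The Welch column is the comparison at matched type I error.

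**Step 4: bounded scores at ρ = 0.5, d = 1.2** (4,000 trials per cell). The scores were 0–12 with mean at 50% of range, 0–12 with mean at 75%, and 0–28 with mean at 60%.

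- Welch t against rank ANCOVA: 74.8 against 85.3, 68.0 against 83.2, 72.9 against 85.2. Gaps are 10.5, 15.2 and 12.3 points.
- Chi-square against rank ANCOVA, in a separate run with SDs of 2.5 and 5 assumed: 79.0 against 86.8, 71.4 against 82.2, 78.2 against 84.9. Gaps are 7.8, 10.8 and 6.7 points.

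**Step 5: other correlations.** Gap in points (rank ANCOVA minus contrast), range over d = 0.5 to 1.2 and both level counts of step 3:

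| ρ | Against Welch t | Against chi-square |
|---|---|---|
| 0.3 | 5.4 to 18.7 | 2.8 to 14.5 |
| 0.5 | 4.9 to 13.9 | 1.7 to 9.6 |
| 0.7 | 3.7 to 9.2 | −0.3 to 4.9 |
| 0.8 | 1.3 to 6.6 | −2.2 to 2.6 |
| 0.9 | −0.2 to 4.1 | −4.8 to 0.6 |

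On the bounded scores at ρ = 0.9, the chi-square version was ahead by 3 to 6 points. The negative entries against chi-square come with that reference's inflated rejection rate.

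**The case against.** The strongest reply is that this is a preference between two legitimate tests. nparLD is a recognised rank method, it fits the stated 2 x 2 design, and its error rate is at worst mildly liberal at 12 per arm. That stands: the issue is efficiency, not validity.

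The reply also has force on size. The SAP gives no correlation or effect size, and a large gap needs a moderate correlation and a large effect. At 0.5 SD and ρ = 0.5, power is only about 17% to 25% by any of these methods. If nparLD is read against a chi-square reference, the visible gap shrinks, though partly because that test rejects too often.

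The scope is inferred too. A reader might conclude that the POMA scores are analysed only by nparLD and never enter the mixed model. The SAP does not say so: it does not list the nonparametric variables, and its mixed-model sentence is not restricted to continuous outcomes. The point therefore applies to whichever scores take the rank route.

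A reader might also infer that a chance baseline difference, through regression to the mean, biases the rank interaction. Under randomisation it does not do so unconditionally, and the null simulations with the Welch reference hold about 5%. The SAP documents no ceiling effect either.

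Last, the SAP is dated 6 April 2021 and the study ran from September to December 2019, so changing the named test now comes after data collection. That is a real cost. It calls for disclosure, but does not remove the efficiency loss.

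**Conclusion.** The point holds as a limited loss of efficiency. For variables analysed with nparLD, baseline is an outcome level and the treatment test is the group-by-time rank contrast.

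With 12 per arm, two-sided 0.05 and ρ = 0.5, all but the sample size assumed, the loss against rank ANCOVA at matched type I error is about 5 points at 0.5 SD and about 10 to 15 points at 0.8 to 1.2 SD. Against the chi-square reference it is about 2 and 6 to 11 points. At ρ = 0.7 it is about 0 to 10 points. At 0.8 to 0.9 it is small, nil or, against the chi-square reference, slightly reversed.

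Two stronger readings are not supported: a general loss of 10 to 15 points, and a loss of at least 5 points for every correlation up to 0.7. Both depend on an effect size and a reference distribution that the SAP does not state.

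**What to change.** In Data management and statistical analysis, name the scores treated as ordinal. For each, make the between-group test a rank ANCOVA: regress the ranked post-intervention score on group and the ranked baseline score, and refer the group coefficient to a t distribution with n − 3 degrees of freedom (21 if all 24 complete both assessments). Keep nparLD as the supporting analysis of group and time profiles. Fix the change before outcomes are analysed by group, and disclose it with its date and reason. If outcomes have already been analysed by group, keep nparLD as the named test and report rank ANCOVA as a labelled sensitivity analysis.

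A proportional-odds model should not be put forward as interchangeable with this test: it has a different estimand and an added assumption, and it was not examined here.

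The cost is revised wording and a few lines of code, with no new data. The downsides are one residual degree of freedom, little or no gain if the correlation is 0.8 to 0.9, and a documented change to the named test after data collection.
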